**1. Introduction and Purpose:**

1. *Describe why this research project will be done. Clearly state the overall objectives, specific aims, hypotheses and rationale for performing the study.*

Preterm birth, defined as birth at less than 37 weeks, affects 11 - 13% of all births in the United States and results in significant morbidity and mortality for the approximately 500,000 infants born preterm each year. The leading cause of preterm birth is preterm labor, and obstetrical interventions have included various tocolytic medications. Efficacy studies on these have yielded disappointing results. (Leveno et al, 1986; Leveno et al 1990; Canadian Preterm Labor Investigators Group, 1992; Leveno and Cunningham, 1992, Mercer and Merlino, 2009). There has been recent interest in nifedipine as a tocolytic for preterm labor (Conde-Agudelo et al, 2011). In 2008, a survey of maternal-fetal medicine specialists reported that 32% were using nifedipine as their tocolytic of choice (Fox et al, 2008), despite that there are no placebo-controlled, randomized studies of nifedipine for acute tocolysis preterm labor showing a benefit.

This is a randomized, double-blinded, placebo-controlled trial of nifedipine for acute tocolysis of preterm labor. Our objective is to determine whether nifedipine decreases the rate of preterm birth. Our null hypothesis is that nifedipine does not reduce the rate of preterm birth.

2. *Indicate the Primary and Secondary Study Endpoints. Also indicate the Primary Safety Endpoints (unless the study is a safety study).*

The primary outcome will be prolongation of pregnancy until at least 37 weeks. Secondary outcomes will include 1) number of patients who receive at least 2 doses of betamethasone, 2) delivery within 48 hours of diagnosis of preterm labor and 3) delivery within 7 days.

3. *Explain why the study risks are reasonable in relation to the potential benefits to subjects and society.*

Given the prevalence of this off-label use of nifedipine, it is unlikely that serious adverse events are commonly encountered. The main serious risk associated with nifedipine is pulmonary edema, but in the 17 reported cases, this risk was reported in the context of other specific risk factors, such as use with other tocolytic drugs, use of rapid-acting formulations, prolonged tocolysis, and use when there was evidence of preexisting maternal cardiac disease/dysfunction. Importantly, in 26 published trials involving isolated use of nifedipine for acute tocolysis, there were no cases of pulmonary edema among patients receiving nifedipine (References 8a-aa).

We plan to restrict use to healthy, normotensive women with singleton pregnancies not receiving additional tocolytic agents. We will also **not** use prolonged or sublingual (rapid acting) administration of nifedipine. Therefore, these reported adverse reactions are most unlikely. Milder side effects associated with nifedipine include headache, flushing and low blood pressure, which resolve with discontinuation of the medication. The balance of benefits and risks favors performing this study to quantify benefits, if any, given the potential for nifedipine to stop preterm labor and its high use rate in the community.

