Women who consent to participate in the above study will be randomized by the IDS pharmacy to receive either placebo or a loading dose of nifedipine 20 mg oral capsule, which will then be repeated after 90 minutes if there are persistent contractions. Four hours after the first dose, they will begin nifedipine 20 mg oral capsule every 4 hours for a total duration of 48 hours, up to a maximum of 160

mg the first 24 hour period (120 mg the second 24 hour period), unless delivery occurs sooner. We anticipate that women will remain on Labor & Delivery for monitoring for at least 24 hours prior to consideration of transfer to the high-risk antepartum unit.

- 3. Include information regarding the study drug(s) classification and the mechanism of action, if known.*

Nifedipine is a dihydropyridine class of calcium channel blocker, and are selective for smooth muscle. The dihydropyridines are thought to inhibit uterine myometrial contractions by causing relaxation of the uterine smooth muscle.

- 4. Include a brief description of outcome variables and study endpoints, as appropriate.*

The primary outcome will be delay of delivery until 37 weeks'. Secondary outcomes will include 1) at least 2 doses of betamethasone, 2) delivery within 48 hours' gestation and 3) delivery within 7 days.

- 5. Indicate the maximum number of local subjects to be consented on this protocol, including projected screen failures and early withdrawals. Include subjects who will receive interventions as well as controls, if applicable. For multi-center research, indicate the total sample size for the entire project across all sites.*

Assuming a 50% consent rate, we will be approaching approximately 300 women for consent. Sample size calculations indicate we need 75 women per arm or 150 total women to demonstrate a 33% reduction in preterm birth, based upon 2 prior Randomized Placebo Controlled Trials of tocolysis (magnesium sulfate and ritodrine) performed at Parkland Hospital (Leveno et al, 1986; Cox and Leveno, 1990).

- 6. If the study involves use of existing charts, records, or specimens, specify the maximum number that will be reviewed to compile the data or the sample population necessary to address the research question.*

This is a prospective trial and existing records will not be reviewed.

- 7. Provide the total number of subjects to be studied at this site and approximately how long the study will last.*

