## 10. Potential Risks:

1. *Describe the known risks and/or potential discomforts associated with each intervention or research procedure. Risks may be physical, psychological, social or economic.*

Mild side effects associated with nifedipine include headache, flushing and low blood pressure, which generally resolve with discontinuation of the medication and without further intervention. In a systematic review, Khan et al (2010) reported that the use of calcium channel blockers for tocolysis or for hypertension in pregnancy was associated with a 3-fold increased risk of tachycardia and an 8 to 9-fold increased risk of hypotension when the dose exceeded 60 mg per day. However, this analysis included all pregnant women receiving all different types of calcium channel blockers (including severely hypertensive women, particularly women with preeclampsia and severe gestational hypertension, a very different population that we propose to study), and thus was not limited to

women with preterm labor, the sub-population than we propose to study. Regarding the possibility of hypotension, Luewan et al (2010) studied blood pressure in normotensive pregnant women treated with nifedipine 10 mg every 15 minutes up to 40 mg, followed by 60 mg controlled release tablet in 4 to 6 hours. The authors defined hypotension as a decrease in diastolic blood pressure of at least 15 mmHg from baseline, and reported up to 17% of patients met these criteria. They concluded that “hypotension secondary to nifedipine was not associated with significant clinical symptoms, suggesting that nifedipine is relatively safe in terms of hypotensive effect.”

Houtzager et al (2006) performed long-term follow-up of children exposed in utero to nifedipine or ritodrine for preterm labor and reported: “The results do not support any differential postnatal effect of the tocolytic agents ritodrine or nifedipine on the child's long-term psychosocial and motor functioning. The slightly better outcome of children randomised in the nifedipine group is most likely due to more favourable perinatal outcomes in this group.”

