#### Moderate Events:

*Hypotension or Tachycardia: **Unlikely***

A review (Chan et al, 2008) of 203 women for whom nifedipine was prescribed as the first-line tocolytic in 212 episodes of preterm labor reported that nifedipine was discontinued for hypotension less than 90/60 in 3 women (1.5%). One woman (0.5%) developed tachycardia of at least 140 BPM.

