#### Severe Events:

##### ***Stillbirth or myocardial infarction: Extremely rare***

Van Veen et al (2005) reported the only identified case of stillbirth in the English language literature after use of nifedipine. Importantly, this patient received multiple tocolytics (atosiban, indomethacin, nifedipine) which will not be the case in our study. Only 2 case reports were found of myocardial infarction associated with nifedipine tocolysis in the literature (Oei et al, 1999; Verhaert and Acker, 2004). In both cases healthy babies were ultimately delivered and there were no abnormalities on maternal follow-up testing. Importantly, in these cases nifedipine was used with another tocolytic (ritodrine), and in one case there were ruptured membranes. We will not be using nifedipine in conjunction with another tocolytic (in this case ritodrine), nor will we be using nifedipine in patients with ruptured membranes (at higher risk for infection). Of note, there have been 3 placebo-controlled trials of nifedipine for maintenance tocolysis over prolonged periods (Lyell et al, 2008; Parry et al, 2012; Roos et al, 2013). Importantly, none of these reported severe adverse events for nifedipine during the long periods that maintenance tocolysis was employed.

3. *Compare the risks of the research to standard of care. If placebo controls are used, justify their use over active or other kinds of controls.*

At Parkland Hospital, patients receive corticosteroids for fetal lung maturity, ampicillin as prophylaxis for Group B streptococcus, sedation and hydration. Tocolytic drugs are not used for preterm labor. However, use of tocolytic agents is within the standard of care for women with preterm labor. Given that it is uncertain whether nifedipine for acute tocolysis results in a benefit by delaying preterm birth and its associated risks, or only carries risks of side effects without benefits, it is ethical to compare nifedipine to placebo.

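### No maternal safety outcome is prespecified, defined or planned for comparison by arm, although the form asks for safety endpoints and hypotension is an expected effect of the drug

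*Combined protocol and SAP*

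**What the plan says.** **Outcomes.** The prompt at Section 1, item 2 says "Also indicate the Primary Safety Endpoints (unless the study is a safety study"). The answer names one efficacy outcome, then states "Secondary outcomes will include 1) number of patients who receive at least 2 doses of betamethasone", adds two delivery-timing outcomes and stops there. Section 3, item 4 repeats the list: "Secondary outcomes will include 1) at least 2 doses of betamethasone, 2) delivery within 48 hours' gestation and 3) delivery within 7 days". Neither list has a maternal safety item.

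**Reason for placebo.** Section 10, item 3 defends the control arm by saying that nifedipine may delay birth "or only carries risks of side effects without benefits, it is ethical to compare nifedipine to placebo".

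**Safety during treatment.** A heart rate above 120 holds a dose and triggers notification (Section 4, item 1). The individual stopping rule includes rash or anaphylaxis, and hypotension if it leads to delivery or to a drug such as ephedrine. Vital signs are monitored regularly on both wards (Section 11, item 2). The data safety monitoring summary has the DSMC watch adverse-event patterns and review safety at every meeting. It then says that safety is evaluated by analysing stoppages of study drug under the stopping rule. The safety criteria for stopping the whole study are stillbirth and emergency delivery for a nonreassuring tracing.

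**Expected hypotension.** Section 10, item 1 cites a review with an "8 to 9-fold increased risk of hypotension when the dose exceeded 60 mg per day", which the plan discounts because it pooled different drugs and populations. It also cites a study in which up to 17% had a diastolic fall of at least 15 mmHg. Section 10, item 2 rates hypotension as unlikely, citing a review of 203 women in which 3 (1.5%) had the drug discontinued for pressure below 90/60.

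**The concern.** The plan asks women to accept placebo or drug because the drug might bring only side effects, yet no planned outcome describes those side effects by arm. Adverse events have no definition, grading, collection schedule or between-arm analysis. Headache and flushing, which the plan expects, have no stated route into the data: Section 4, item 4 plans no questionnaires, and Section 8 names a routine database of obstetrical and neonatal outcomes.

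The one safety method that is spelled out counts hypotension only after a clinician has acted on it. Such events are rare in the plan's own sources, so that comparison would tell almost nothing in a trial of this size. If the primary outcome shows no benefit, the report could then say little about what the exposed women experienced. With no prior definition, any side-effect table would also be open to choice after the data are seen.

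**Working it through.** **1. The plan's own sample size.** Inputs from Section 14, item 2: 71.2% v 47.5%, two-sided alpha 0.05, power 80%. The mean proportion is 0.5935.

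- Uncorrected: n = [1.96·√(2·0.5935·0.4065) + 0.8416·√(0.712·0.288 + 0.475·0.525)]² / 0.237² = (1.3615 + 0.5674)² / 0.05617 = 66.2, so 67 per arm.
- With continuity correction: (66.2/4)·[1 + √(1 + 4/(66.2·0.237))]² = 74.4, so 75 per arm.

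The stated 75 per arm is reproduced and is not in dispute. It is used below with the chi-squared test that Section 14, item 1 names for categorical variables.

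**2. Hypotension counted only when acted on.** The input is the plan's 3/203 = 1.48%, stated as 1.5%. This is a discontinuation rate, used as the nearest available stand-in for the stopping-rule event. The documents give no placebo rate, so 0 to 0.5% is assumed.

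- Expected events on nifedipine: 75 × 0.0148 = 1.1.
- Chance of none: 0.985^75 = 0.32.
- Events needed against 0 on placebo: 3 v 0 gives z = 0.040/√(0.020·0.980·2/75) = 1.75, not significant. 4 v 0 gives z = 0.0533/√(0.0267·0.9733·2/75) = 2.03, significant. At least 4 events are needed where about 1 is expected.
- Exact power (full enumeration): 2.5% against 0 and 1.8% against 0.5%. Fisher's test gives about 0.1% or less.

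**3. Hypotension counted from readings.** The input is the plan's figure of up to 17% for a diastolic fall of at least 15 mmHg, or 75 × 0.17 = 12.75 events. Placebo rates are assumptions.

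| Nifedipine v assumed placebo | Chi-squared, exact | Fisher, exact | Normal approximation |
|---|---|---|---|
| 17% v 2% | 94% | 88% | 89% |
| 17% v 5% | 68% | 58% | 65% |
| 17% v 8% | 39% | 30% | 38% |

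Example of the approximation, 17% v 5%: Φ{[0.12·√75 − 1.96·√(2·0.11·0.89)] / √(0.17·0.83 + 0.05·0.95)} = Φ{(1.0392 − 0.8673)/0.4343} = Φ(0.396) = 0.65.

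**4. Other expected effects.** Section 10, item 2 cites flushing up to 71% and headache 25% in one study, and 4.4% for flushing and for moderate headache in another. Exact chi-squared power is over 99% for flushing at 71% v an assumed 10%, 70% for headache at 25% v an assumed 10%, and 22% for either at 4.4% v an assumed 1%.

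**5. What has no figure.** The documents give no rate for readings below systolic 90 or diastolic 50, so no power can be stated for that definition.

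**The case against.** The plan is not silent on maternal safety. Vital signs are watched, a fast heart rate holds a dose, rash or anaphylaxis ends participation, and the DSMC sees adverse-event patterns. Held doses, stoppages and reported events could be tabulated by arm. That stands, so a reader who infers that nothing is measured goes too far. What is missing is definition, prespecification and a planned comparison.

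Four other inferences are tempting and are not supported:

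- **That the gap could never be filled at analysis.** Section 3, item 6 says "This is a prospective trial and existing records will not be reviewed", and Section 8 is similar. Both answer prompts about records that already exist. They do not bar vital signs charted during dosing, and Section 8 does not call the database the only source.
- **That the trial fails its stated objective.** The objective in Section 1 is efficacy. The side-effect remark in Section 10 is an argument for equipoise.
- **That hypotension is the commonest harm.** By the plan's own figures flushing and headache are more frequent.
- **That the risk text hides the higher rate.** Section 10 already describes the 1.5% as discontinuation and already reports the 17%.

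The 17% is also an upper figure from another regimen (10 mg every 15 minutes up to 40 mg, then a 60 mg controlled-release tablet), and every placebo rate above is assumed. These limits qualify the size of the gain from a reading-based measure. They do not alter the absence of a safety outcome.

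**Conclusion.** The point holds as an omission in the outcome plan, and it should be corrected. The form asks for safety endpoints, none is given, and the only evaluation method described relies on events too rare to inform: about one expected on nifedipine and about 2 to 3% power. A measure taken from readings could be informative at the same sample size, with 39% to 94% power by chi-squared across assumed placebo rates of 8% to 2%, if the 17% carries over to this regimen. The comparison of definitions rests on those assumptions. The finding that no maternal safety outcome is prespecified rests on none of them. The primary analysis and the sample size are unaffected.

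**What to change.** Add maternal safety outcomes to Section 1, item 2 and Section 3, item 4, assessed over the 48-hour dosing period and reported by arm with confidence intervals:

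- hypotension from charted readings, defined as systolic below 90 or diastolic below 50 mmHg (the plan's own entry limits);
- a diastolic fall of at least 15 mmHg from baseline (the definition in the study cited in Section 10);
- pulse above 120;
- held doses and stopped treatment, with reason;
- headache and flushing where charted.

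State in Section 8 that vital signs charted prospectively during dosing are trial data. Estimates with intervals should be the main presentation, because power is modest for several of these.

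These are measurement definitions only. No hold, stopping or dosing rule changes. Section 4 puts the hold limit at a heart rate above 120 while Section 10, item 1 describes it as 120 or more, and the sponsor should reconcile the two.

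The cost is outcome wording plus extraction from charts for 150 women. No new procedure or visit is needed. Headache and flushing will be under-recorded if they depend on routine charting, and the report should say so.

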#### **4. Study Procedures:**

- 1. Provide a chronological description of all study procedures. If applicable, divide procedures into pilot, screening, and procedures performed at each regular visit. Indicate how many total visits and approximately how long visits will last. For studies that are providing medication(s), give the name(s), dosage, and route of administration. For studies that have more than one arm/part, provide the above information for each.*

Women presenting with symptoms of preterm labor will be assessed using electronic external fetal heart rate and uterine contraction monitoring. Women will receive a baseline and subsequent cervical exams as necessary. If at any time during her evaluation, the woman is dilated to at least 2 cm and has uterine contractions, she will be potentially eligible for study. Women with a singleton gestation between 28-0/7 weeks and 33-6/7 will be approached for consent to participate by Research Nurses employed by the Department of Obstetrics & Gynecology or [name] if a Research Nurse is unavailable. They will be randomized by the IDS Pharmacy into treatment (study drug, nifedipine) or control (placebo) groups.

Study women will receive nifedipine 20 mg or placebo oral capsule followed by a second dose after 90 minutes if there are persistent contractions. Four hours after the initial dose, they will begin nifedipine 20 mg or placebo oral capsule every 4 hours for a total duration of 48 hours, up to a maximum of 160 mg the first 24 hour period (120 mg the second 24 hour period), unless delivery occurs sooner. We anticipate that women will remain on Labor & Delivery for monitoring for at least 24 hours prior to consideration of transfer to the high-risk antepartum unit.

There will be a "HOLD DOSE" parameter in which a dose will be held if an enrolled patient:

- refuses medication
- has heart rate greater than 120

If a dose is held, the nurse will contact the 4th year resident who will ensure [name] is notified.

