## **6. Criteria for Inclusion of Subjects:**

1. *Describe the characteristics of the subject population. For example, list any characteristics required for eligibility, such as diagnosis, prior therapy, age, or gender.*

Inclusion criteria include:

- Mothers between 16 and 44 years of age inclusive.
- Singleton pregnancy
- Intact membranes
- Between 28-0/7 weeks and 33-6/7 weeks' gestation inclusive
- Reported or documented uterine activity
- Cervical dilation between 2 cm and 4 cm inclusive

2. *Explain the rationale for the use of special classes of subjects who are more likely to be vulnerable, such as pregnant women, children, cognitively impaired people or prisoners.*

Pregnant women are included as this study is for an intervention for preterm labor.

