Fortunately, 2 prior Randomized, (placebo) Controlled Trials (RCT) of tocolysis (magnesium and ritodrine) from Parkland Hospital have been published. For the RCT by Leveno et al of ritodrine versus placebo (“Single-Centre Randomised Trial of Ritodrine Hydrochloride for Preterm Labour”, Lancet, 1986) in which women with singleton pregnancies and preterm labor with cervical dilation up to 4 cm, 39 of 52 (75%) patients randomized to the control group delivered between 27 and 35 completed weeks. Similarly, for the RCT of magnesium sulfate versus placebo by Cox and Leveno (“Randomized investigation of magnesium sulfate for prevention of preterm birth” Am J Obstet Gynecol 1990) in which women with singleton pregnancies and preterm labor with cervical dilation less than 5 cm, 55 of 80 (68.8%) of patients randomized to the control group delivered between 27 and 35 completed weeks’ gestation. These are important data derived from randomized, placebo-controlled, prospective trials done here at Parkland Hospital and we feel that our sample size should incorporate this prospectively obtained data. An average of the above preterm birth rates for these two RCTs at Parkland Hospital is 71.2% (39+55 / 52+80). In slight distinction to the above studies, for the current study, we are including women beginning at 28 weeks’ gestation, and we will be assessing preterm birth as delivery at less than 37 weeks. In theory, the preterm labor rate for delivery at less than 37 weeks (the primary outcome of the current trial) would be higher than this average preterm birth rate for women prior to 35 completed weeks’ gestation. However, using these prospectively obtained numbers from past studies of preterm labor at Parkland hospital, we would need approximately 150 women (75 women in each of the 2 arms) in order to detect a 1/3 reduction (from 71.2% to 47.5%) in the rate of preterm birth with 80% power and an alpha of 5%.

Analysis of internal obstetrics operations data indicates that for the month of March 2015, there were 10 women between 28-0/7 weeks and 33-6/7 weeks with preterm labor and a cervix of 2 to 4 cm dilation. Of these 10 women, 6 were ineligible for participation in the study (2 had diabetes in pregnancy, 1 women had a twin gestation, 1 women was only 15 years of age and 1 woman had bleeding concerning for abruption). Of the 4 eligible women in March of 2015, 2 elected to participate in the study, consistent with our ongoing consent rate of approximately 50%.

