Effective September 17, 2015, there has been a protocol change at the level of the Division of Maternal-Fetal Medicine at Parkland Hospital. This protocol change will be to give corticosteroids for fetal lung maturity to women with diabetes and to all women with hypertension who are at risk of preterm birth. This MFM Division level protocol change will affect this study of women at risk of preterm birth.

Given that 2 of the formerly ineligible women (due to diabetes) who presented in March 2015 would now be eligible due to the above protocol change, we estimate that up to 24 additional women (2 x 12 = 24) would be screened per year, and up to 12 additional women (50% of the 24 additional screened) would participate. Given that there were 29 women recruited over the initial 13 months (which equates to approximately 27 over 12 months), under the new practice in which corticosteroids will be given more broadly (and women with diabetes and mild hypertension not treated with medications are eligible for participation), we estimate that up to 78-90 women would now be screened, and of these, we estimate that 39-40 women would participate per year.

Therefore, over ~4-5 years, we would expect 300 patients screened and 150 patients consented. In order to detect a 33% reduction in the rate of preterm birth less than 37 weeks’ gestation, assuming 80% power and a 2-sided alpha of 5%, a sample size of 75 patients per arm (two arms, study drug and placebo), 150 patients total, will need to be recruited. So far in the current study, we have had about a 50% consent rate. Assuming a 50% recruiting rate (50% x 300 = 150), it is estimated that this study will take 4 to 5 years to complete.

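### Do the 48-hour and 7-day delivery outcomes need a new time origin because one is counted from diagnosis and the other states none?

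*Combined protocol and SAP*

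**What the plan says.** Section 1, item 2, lists three secondary outcomes. The second is "delivery within 48 hours of diagnosis of preterm labor". The third is delivery within 7 days, with no origin of its own. Section 3, item 4, whose form prompt asks only for a brief description, restates them as "2) delivery within 48 hours' gestation and 3) delivery within 7 days". No other section defines either outcome, and Section 14 names the tests without giving a window or an origin.

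Section 4 gives the order of events. If at any point in her evaluation "the woman is dilated to at least 2 cm and has uterine contractions, she will be potentially eligible for study". Consent is then sought, and of the consenting women the section says: "They will be randomized by the IDS Pharmacy into treatment (study drug, nifedipine) or control (placebo) groups". Maintenance capsules start four hours after the first dose and are given "every 4 hours for a total duration of 48 hours". Section 2, item 5, describes preterm labor as cervical dilatation with contractions. Section 6 lists "Reported or documented uterine activity" among the entry criteria.

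**The concern.** Three things look wrong together.

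- The 48-hour clock starts at diagnosis, before allocation. Each woman's window contains a lead-in of varying length in which, as a randomised woman, she cannot have delivered. The window also closes before a full 48-hour course can end.
- The Section 3 wording cannot be applied as written, and the 7-day outcome has no stated start in either place.
- No sentence says which examination or note gives the time of diagnosis, although cervical examinations may be repeated.

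If these were real defects, two analysts could classify the same delivery differently, the origin could be settled after results were seen, and events would be lost from the outcome closest to the trial's stated purpose of gaining time for corticosteroids.

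**Working it through.** **1. Is there a conflict between sections?** Set side by side:

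| Outcome | Section 1, item 2 | Section 3, item 4 |
|---|---|---|
| 48 hours | counted from diagnosis | garbled, no rival origin |
| 7 days | no origin; follows the 48-hour item in the same list | no origin |

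Only one origin appears anywhere, and it is diagnosis. Section 3 offers no alternative clock. The two sections therefore do not send an analyst to different answers: one gives the definition and the other miscopies it. Suppose a woman is randomised 6 h after diagnosis and delivers 45 h after randomisation. She is at 6 + 45 = 51 h on the diagnosis clock, so she is not a 48-hour event. She would be one on a randomisation clock, but no section contains that clock. The example shows what a new definition would change, not a contradiction in this one.

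**2. Can diagnosis be timed?** Section 2 describes preterm labor as dilatation with contractions, and Section 4 makes a woman potentially eligible at 2 cm or more with contractions. The first examination that meets this is a workable time of diagnosis. It is made before allocation.

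**3. Does the early clock bias the arms?** The lag from diagnosis to randomisation is a pre-allocation quantity, so randomisation balances it in expectation, and treatment is blinded. Both windows are shortened in the same way.

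**4. What precision is lost?** From the documents: 75 per arm, two-sided 5%, and a planned one-third reduction ("in order to detect a 1/3 reduction (from 71.2% to 47.5%) in the rate of preterm birth", Section 14, item 2). The plan's own figure reproduces. For 71.2% against 47.5% at 80% power, the pooled-variance normal formula gives 67 per arm, and 75 with the continuity correction. That calculation concerns the primary outcome only.

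Assumed, because the documents give neither: the lag d, the delivery rates, and a constant hazard after randomisation. If p is the probability of delivery within T hours of randomisation, the probability inside a window that opened d hours earlier is

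p(d) = 1 − (1 − p)^((T − d)/T).

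For T = 48 and d = 6 the exponent is 42/48 = 0.875. Control: 1 − 0.75^0.875 = 0.223. Nifedipine at a one-third reduction: 1 − 0.8333^0.875 = 0.148. Power is the normal approximation for two proportions, with pooled variance under the null and no continuity correction:

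| Assumed rates | d = 0 | 3 h | 6 h | 12 h |
|---|---|---|---|---|
| 48 h, 25% vs 16.7% | 24% | 23% | 22% | 20% |
| 48 h, 25% vs 10% | 68% | 65% | 63% | 56% |
| 48 h, 25% vs 10%, early clustering (Weibull shape 0.5) | 68% | 67% | 65% | 62% |

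For the 7-day outcome (T = 168 h, 50% vs 33.3%), power goes from 54.5% to 53.4% at 6 h.

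The relative risk barely moves. At 25% vs 10% it is 0.400 with no lag and 0.194 vs 0.076, or 0.39, at 12 h. Expected control events at 6 h fall from 75 × 0.25 = 18.8 to 75 × 0.223 = 16.7, about two women.

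**The case for a change.** The strongest contrary case is that randomisation is one discrete event per woman, that counting from it removes the lead-in, and that stating it for both outcomes would close off any later choice of origin. It would take two sentence edits and a recorded time. The outcome also matters, because delay for corticosteroids is the declared purpose in Section 2.

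Part of this stands. The Section 3 phrase is wrong as written, the 7-day origin has to be inferred, and a sentence naming the diagnostic examination would be tidier. The rest does not amount to a need:

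- A randomisation clock would not line up with the course either. Dosing runs from the first capsule, so that window would also close early, by the gap from randomisation to first dose.
- An interval from diagnosis is a legitimate clinical measure.
- A change would reach back to women already enrolled ("Given that there were 29 women recruited over the initial 13 months"). The documents do not say that randomisation times are recorded.
- The largest losses in the table need a 60% reduction (25% to 10%) and a 12-hour lag. The first is well above the plan's one third, and nothing in the documents supports the second.
- Low power at one third is present with no lag at all, so it is not a consequence of the clock.

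The lack of a named neonatal morbidity endpoint, although Section 2 mentions morbidity, is a separate request for an addition and has no bearing on the time origin.

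**Conclusion.** The concern does not call for a change. The plan states one origin for the 48-hour outcome. The Section 3 wording is a clerical slip, and the 7-day origin is a gap that an analyst would fill sensibly by carrying diagnosis forward. Followed as written, the comparison is unbiased. The loss is about 2 power points at 48 hours and 1 point at 7 days for an assumed 6-hour lag and a one-third effect, and the relative risk is essentially unchanged. These figures rest on assumed rates, an assumed lag and a constant hazard. A long lag combined with a large effect would cost more (68% to 56% at 12 h), but still without bias. Only secondary outcomes for which no power is claimed are involved; the 37-week primary outcome and the 75 per arm are unaffected. Preferring randomisation to diagnosis as the starting point is a matter of choice with negligible gain.
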